4.10 Study Flow

See Procedural Flow Chart (Section 14), Screening Flow Chart (Section 15) and Study Assessment Table (Section 16).

5. Enrollment Procedures

The Vanderbilt-Ingram Cancer Center (VICC) Coordinating Center will coordinate enrollment in the study.

Prior to registration, a copy of the IRB approval at the site will be kept on file at the Vanderbilt-Ingram Cancer Center (VICC) Coordinating Center. Eligible participants will be entered on study centrally in OnCore at the VICC Coordinating Center.

All patients MUST be registered with the Vanderbilt-Ingram Cancer Center (VICC) prior to the start of study procedures such as tissue acquisition. Registration can only be conducted during the business hours of 8AM – 5PM Central Time, Monday through Friday.

CONFIDENTIAL

Enrollment Process:

Potential patients will be screened using the REDCap VERITAS e-Eligibility tool. Eligible patients will be approached by key study personnel either in person or via phone. Patients who agree to participate will provide signed research informed consent. This can be accomplished using a printed paper consent form which is then scanned and uploaded to VERITAS e-Eligibility upon completion, or electronically via the e-consent module embedded within VERITAS e-Eligibility, in which patients may sign research informed consent electronically (either in clinic or after the e-consent form is emailed to them following full informed consent discussion from key study personnel over the phone). Once signed research informed consent has been obtained, a record for the subject is created in the REDCap VERITAS database. Central adjudication are performed within three business days as described in section 4.5, with determinations entered into the VERITAS database. Once central adjudication is complete, the subject's e-eligibility CRF part 2 is completed indicating whether they are eligible for randomization after central adjudication. Eligible patients are then randomized via a randomization module embedded within the VERITAS database.

Note:

Upon satisfactory review of eligibility documents submitted, the Coordinating Center will approve enrollment and issue a subject ID number if one was not issued at screening. Once registration/enrollment confirmation from Coordinating Center is received, proceed with protocol procedures.

Please contact the assigned Study Contact with any questions regarding this process. You can also reach out to your assigned CRA once the study is activated.

The VICC Coordinating Center will assign Subject ID numbers to all patients whose eligibility has been confirmed. Only patients deemed eligible will be registered to the study. Sequence/study ID numbers will not be re-used if a patient screen fails. Following registration, eligible participants should begin the study consistent with the protocol no later than 28 days after registration/enrollment by the VICC Coordinating Center.

Following registration, eligible participants should initiate navigation bronchoscopy or CT-guided biopsy no later than 30 business days after the site is notified of randomization by the VICC Coordinating Center. If a participant does not receive the procedure following randomization within the allowed time period, the patient may be re-consented or participant's registration on the study will be canceled. The Study Contact should be notified of cancellations as soon as possible.

The purpose of this 30 business day scheduling window is to protect subjects from being randomized to a procedure which overly delays their care, when the alternative procedure could be performed substantially sooner and would otherwise have been utilized in clinical practice outside of this trial. For example, if biopsy procedure #1 cannot be performed for 8 weeks due to local factors (equipment failure, perhaps), but biopsy procedure #2 could be performed within two weeks, the 30-day window protects this patient from a potentially harmful delay in a malignant diagnosis by removing them from the trial so they may proceed with procedure #2 on clinical grounds. However, if a situation arises in which a patient must be scheduled outside the 30-day window but 1) the alternative procedure cannot be performed meaningfully sooner and 2) the delay in biopsy is

CONFIDENTIAL

not expected to impact any eligibility criteria, the patient may remain in the trial (an example in which point #2 might be invoked: a patient with a 29 mm nodule delayed for 3 months, a sufficiently long interval of time in which the nodule may well have grown to exceed 30 mm diameter and therefore no longer be eligible for the trial). This determination must be agreed upon by both the local PI and the central PI ([name]) and will be documented in the "notes" field at the end of REDCap CRF #1.

As is generally accepted, standard of care procedures performed prior to consent, but within the protocol defined screening window for each assessment, can be used for study purposes. All research-only procedures must be performed after patient consent.

Subjects who provide informed consent, but are determined to be ineligible prior to initiation of navigation bronchoscopy or CT-guided biopsy will be considered screen failures and the reason for screen failure will be documented. Subjects who fail to present to their assigned procedure after randomization will be considered screen failures as well. Subjects who present to their assigned procedure but do not undergo the procedure for reasons other than safety will be analyzed on an intention-to-treat basis (see above Section 4.7 for details).

6. Methodology

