4.2 Patient Inclusion and Exclusion Criteria

Inclusion criteria:

1. Patient is \geq 18 years of age at time of signing informed consent .
2. Patient is referred for biopsy of a single indeterminate pulmonary nodule, with the following characteristics regarding size, location, accessibility, and probability of malignancy:
 - a) Intermediate or high pre-test probability of malignancy as defined by a pre-test probability of malignancy between 10% and 100%, using a validated clinical prediction model, which is either:
 - i. The Brock model¹⁴ if no PET scan data are available, or
 - ii. The Herder model¹⁵ if PET-CT data are available.
 - b) Size between 10 and 30 mm (long diameter).
 - c) Location peripheral, here defined as occupying the middle or outer third lung zones.
 - d) Accessible via navigation bronchoscopy and also accessible via CT-guided biopsy (i.e. the nodule is clinically suited to equal access by either procedure), as confirmed by an independent interventional panel (see Section 4.5).

Note: Prior to randomization, the main purpose of this study-provided central review is to establish panel agreement with local expertise offered by the participating study site, that local management of a consented candidate patient at the site can be achieved by standard of care navigation

CONFIDENTIAL

bronchoscopy or equally achieved by standard of care CT-guided biopsy (with either procedure able to be performed at the local institution).

Exclusion criteria:

1. Patients with proximal nodules, as defined by nodules present in the proximal 1/3 of the lung by dedicated software analysis (described below) will not be eligible for the study.
2. Patients with multiple nodules requiring biopsy (patients may have other nodules not considered for biopsy).
3. Radiologically abnormal mediastinal or hilar lymph nodes requiring endobronchial ultrasound.
4. Patients for whom stereotactic body radiation therapy is planned even if biopsies show no evidence of malignancy.
5. Patients with contraindication to biopsy or deep sedation/general anesthesia.
6. Patients unable or unwilling to comply with study follow-up schedule.
7. Patients previously randomized to the study.
8. Patients unable to provide documented informed consent.
9. Patients who are nursing or pregnant as verified by an optional standard of care pregnancy test. (Testing required only if deemed clinically necessary by the patient's study physician.)

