6.1 Statistical methodology

This study will be a randomized controlled trial of navigation bronchoscopy vs. CT-guided biopsy using a non-inferiority study design. The hypothesis of the study is that the diagnostic accuracy of EMN navigation bronchoscopy using the SuperDimension platform with F-Nav performed by interventional pulmonologists is non-inferior to the diagnostic accuracy of CT-guided biopsy performed by interventional radiologists. Eligible patients will be randomized on a 1:1 basis and the randomization will be stratified by the following two criteria within each center to provide balance between treatment arms on these features:

1. Location in the middle or outer third of the lung
2. Pre-test probability of malignancy (50% or less VS 51% or more)

Within each stratum, block sizes of 2 and 4 will be used to enhance blinding.

Though the primary analysis will use a Bayesian approach, the initial power analysis uses a Frequentist approach. We assume that a diagnostic accuracy for CT-guided biopsy is 90%. The non-inferiority margin is set at 10 percentage points, and one-sided type I error rate is set at 5%. Thus, if the true diagnostic accuracy for navigation bronchoscopy is lower than 80%, we will have 5% probability (type I error rate) to incorrectly conclude noninferiority. With this parameter setting a sample size of 112 per group will give approximately 80% power if the true diagnostic accuracies are 90% for both arms. Considering an attrition rate of 15%, the sample size is 129 per group (258 total). Large volume centers could be expected to enroll 50 patients per year, therefore 6 centers are necessary. One year recruitment plus one year follow-up represents 2 years of recruitment time. The noninferiority margin has been chosen based on the known pneumothorax rate of CT

CONFIDENTIAL

biopsy which is in excess of 10%, and after polling a number of clinicians who are involved in the diagnostic workup of patients with lung nodules, where this margin was considered reasonable.

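### Nothing before randomisation checks that both procedures can be scheduled in time, so removal under the Section 5 window can depend on the allocated arm

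*Combined protocol and SAP*

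**What the plan says.** **Before randomisation.** Section 4.5 has a two-person panel judge the technical feasibility of each route. The note to inclusion criterion 2(d) in Section 4.2 adds a site condition: "with either procedure able to be performed at the local institution". Section 5 has e-Eligibility CRF part 2 completed after central adjudication, and the randomisation module follows. None of these mentions dates or waiting times. The flow charts in Sections 14 and 15 are not shown in the text available, and the items of CRF part 2 are not reproduced.

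**After randomisation.** Under Section 5 the clock starts when the site is notified of randomisation, and it concerns the assigned procedure. If that procedure is not done in time, the patient may be re-consented or the registration is cancelled. The stated rationale is patient protection: "the 30-day window protects this patient from a potentially harmful delay in a malignant diagnosis by removing them from the trial". A patient outside the window may stay if the other procedure is not meaningfully quicker and the delay should not affect eligibility. "This determination must be agreed upon by both the local PI and the central PI", and it is recorded in a notes field.

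**Analysis.** Section 6.2 makes the per-protocol set primary and intention-to-treat (ITT) a sensitivity analysis.

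**The concern.** Randomisation protects the comparison only while patients stay in, or leave, for reasons unrelated to their arm. Here the trigger for leaving is slowness of the procedure that was drawn, and the retention exception then asks whether the other procedure is faster. Patients with unequal access therefore tend to leave the slower arm and stay in the faster one. Those who decide on exceptions necessarily know the allocation. Stratifying by centre does not help, because the removal comes afterwards.

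If patients with slow access to one procedure also differ in how likely that procedure is to succeed, the retained groups are no longer comparable and the non-inferiority conclusion can be biased. Timely access to both routes is, at least in part, an eligibility matter that could be asked before allocation.

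**Working it through.** **1. The protocol's own example, by allocation** (procedure #1 in 8 weeks, #2 within two weeks)

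| Draw | Assigned procedure in window? | Other procedure sooner? | Result under Section 5 |
|---|---|---|---|
| #1 | No | Yes | Removed, has #2 outside the trial |
| #2 | Yes | Not asked | Stays |

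The patient is the same in both rows; only the draw differs.

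**2. The plan's figures reproduced.** Inputs from Section 6.1: 90% accuracy in both arms, one-sided 5% error, 1:1 allocation, and "The non-inferiority margin is set at 10 percentage points".

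n = (1.645 + 0.842)² × (0.9×0.1 + 0.9×0.1) / 0.10² = 111.3, so 112 per group. This agrees with the statement that "a sample size of 112 per group will give approximately 80% power if the true diagnostic accuracies are 90% for both arms". The allowance for attrition is 112 × 1.15 = 128.8, so 129 per group.

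The Section 6.2 decision rule (Beta(1,1) priors, non-inferior if the posterior probability of inferiority by more than 10 points is below 5%) was enumerated exactly at fixed true rates with 112 per arm. It gives 80.1% power at 90/90 and a 5.3% false non-inferiority rate at NB 80%, CT 90%.

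**3. Effect of selective removal.** The documents give no removal rate, so these are assumptions: 10% of the navigation bronchoscopy (NB) arm is removed, none of the CT arm, and true NB accuracy among all randomised is 80% against CT 90%. If the removed patients would have had accuracy a, the retained NB rate is (0.80 − 0.10a) / 0.90. The evaluable NB number from 129 is 129 × 0.90 = 116.

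| a | Retained NB rate | False non-inferiority, 112 v 112 | NB 116 v CT 129 |
|---|---|---|---|
| 60% | 0.74/0.90 = 82.2% | 12.7% | 13.2% |
| 70% | 0.73/0.90 = 81.1% | 8.3% | 8.5% |
| 80% (no difference) | 0.72/0.90 = 80.0% | 5.3% | 5.3% |
| 90% | 0.71/0.90 = 78.9% | 3.2% | 3.2% |

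Size and sign both depend on a, which the documents do not inform. If removals fall on CT instead, the direction mirrors.

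**4. Power.** If removal is unrelated to outcome, the same rule at 90/90 gives 84.8% with 129 v 129 and 82% with NB 116 v CT 129. Both exceed the planned 80%.

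**5. Would ITT repair it?** Section 6.2 counts randomised patients who drop out without final data as failures, but the text does not say whether a cancelled registration is one of these. If it is, with 129 per arm and true 90/90, the NB rate becomes 0.9 × (1 − r). The chance of concluding non-inferiority falls from 84.8% to 68.2%, 39.0% and 8.2% for r = 2%, 5% and 10%. That analysis penalises the arm with removals; it does not recover the missing biopsy results.

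**The case against.** The case against has real force on several points, and a reader could easily infer more than the text supports.

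- *Removal is automatic and looks only at the assigned arm.* It is not automatic: re-consent or a documented exception is possible. The trigger is the assigned procedure, but the rule then compares it with the other one. That comparison does not remove the dependence on allocation, since the patients who leave are those for whom the other arm is quicker.
- *Most such delays could be foreseen.* The documents do not show this. The one cause offered is a possible equipment failure, which a check before randomisation may miss.
- *The bronchoscopy arm will lose more patients.* Section 4.6 requires general anaesthesia and a specialised platform, which makes longer waits plausible, but no waiting times are given. The operator volume required is higher for bronchoscopy (more than 100 procedures) than for CT (more than 25 per department).
- *The removed patients are harder cases.* Patients with contraindications to biopsy or anaesthesia, and nodules judged unreachable, are already excluded. An equipment failure would not select difficult nodules.
- *The trial loses power.* A fall to 76.7% appears only with 100 NB against 112 CT patients, that is, removals on top of a fully used attrition allowance. Starting from 129 per arm, power stays about 82%.

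A check shown only in the unseen flow charts or CRF items also cannot be ruled out. What survives is narrower: the readable text has no such check, and the protocol's own example makes retention depend on the draw.

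**Conclusion.** The point holds as a design weakness with a cheap remedy. Exclusion after randomisation can depend on allocation, and the per-protocol primary analysis leaves those patients out. No stated sample size, margin or error rate is wrong because of it.

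Whether it biases the result is unknown. That requires slow access to be related to diagnostic accuracy, and the documents give no removal rate, no direction by arm and no such link. Under the assumed 10% removal from the NB arm, the false non-inferiority rate ranges from about 3% to about 13% around a baseline of 5.3%, according to how the removed patients would have fared. The documents support neither a claim that the error is inflated nor a claim of material power loss; they support only that the design leaves the comparison open to this kind of selection.

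**What to change.** 1. Add to criterion 2(d) in Section 4.2 and to e-Eligibility CRF part 2, completed before the randomisation module opens: *the site confirms that both navigation bronchoscopy and CT-guided biopsy can currently be scheduled within the protocol window*. Record patients who fail this as screen failures before randomisation.
2. Leave the post-randomisation patient-protection rule as it is. Log every cancellation, re-consent and exception by arm, with the reason and the dates available for both procedures.
3. Reconcile the statements of the window so that the check has one meaning. Section 4.5 gives 3 weeks and, in the same phrase, 30 calendar days. Section 5 gives 30 business days (six working weeks, about 42 calendar days), refers to a 30-day window, and separately sets 28 days from registration to begin the study. Which is intended is for the sponsor to settle.

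The cost is one scheduling enquiry per patient and a few patients screened out before randomisation. The sample size and margin do not change. The check will not catch unforeseen events, which is why the log is needed as well.

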4.6 Intervention Arm: Bronchoscopy Pathway

The intervention arm will consist of electromagnetic (EMN) navigation bronchoscopy using the Medtronic SuperDimension platform with F-Nav. Patients' available DICOM CT images will be uploaded into the planning software. CTs obtained more than 21 days before the planned procedure, and CT not meeting minimal technical requirements for optimal roadmap planning (adequate CT reconstructions and slice thickness of 1.5mm or less) will be repeated before the procedure. Bronchoscopy will be performed by interventional pulmonologists with expertise in navigation bronchoscopy (as defined by more than 100 procedures performed in the past 2 years, with at least 25 of these performed with F-Nav). Procedures will be performed under general anesthesia with neuromuscular blockade (to facilitate breath holds required for FNAV image acquisition) in a dedicated bronchoscopy suite or operating room. Bronchoscopy will be performed as previously described with confirmation by radial ultrasound.¹⁷ Suggested intraprocedural flow is detailed in the figure in section #14. Radial ultrasound will be used for confirmation only, and not as a navigational tool (i.e. catheters not aligned with the registered target will be considered non-diagnostic). Biopsies will be obtained using a any-gauge needle, with at least 5 passes obtained per nodule. Forceps biopsies, brushings or other biopsy tools will be performed according to the procedure algorithm. Rapid on-site evaluation will be performed to assess for specimen adequacy. All procedures will be followed by fluoroscopy evaluation of the chest to exclude pneumothorax, and, if indicated, ultrasound and/or formal chest radiograph as per standard of care. The procedure will be deemed non-diagnostic if the proceduralist is unable to reach the nodule or if a complication occurs and therefore no biopsy is obtained.

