4.7 Comparison: CT-guided Biopsy Pathway

The control arm of the study will consist of CT-guided biopsy, which will be performed by interventional radiologists with expertise in transthoracic needle biopsy and/or fine needle aspiration (as defined by more than 25 procedures performed in the past two years as a department). Procedures will be performed in a dedicated interventional CT scanner with multi-slice capabilities. Patient analgesia with local anesthesia and moderate conscious sedation will be used. Biopsy number, core biopsy vs. fine needle aspiration, use of coaxial needles, and use of rapid on-site cytologic examination will be at the discretion of the proceduralist per local institutional preferences. Procedures will be followed by limited CT scan and/or chest radiograph to exclude pneumothorax if required per local standard of care. The procedure will be deemed non-diagnostic if the proceduralist is unable to reach the nodule or if a complication occurs and therefore no biopsy is obtained.

- 1. Patients not eligible for general deep sedation and general anesthesia and therefore not eligible for bronchoscopy, but potentially eligible for CT-guided biopsy, will be excluded from the study but recorded as such in the CONSORT diagram.**
- 2. Patients randomized who fail to present for their assigned intervention will be considered screen-failure**
- 3. Patients randomized who present for their assigned intervention but do not undergo the procedure for reasons other than for contraindications to the procedure (per institutional policy) will be analyzed as non-diagnostic procedure, and otherwise considered screen-failure. The cause for cancellation will be recorded in the case report form.**

CONFIDENTIAL

See Procedural Flow Chart (Section 14).

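### A randomised patient who attends but is stopped for safety before tissue is taken can be scored non-diagnostic or dropped, because Sections 4.6, 4.7 and 5 use different, undefined terms

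*Combined protocol and SAP*

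**What the plan says.** Three rules in the protocol cover a randomised patient who attends and leaves without tissue.

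- **Sections 4.6 and 4.7, procedure paragraphs (same sentence for both arms).** The procedure is non-diagnostic if the nodule cannot be reached or "if a complication occurs and therefore no biopsy is obtained".
- **Section 4.7, item 3.** Attendees who "do not undergo the procedure for reasons other than for contraindications to the procedure (per institutional policy) will be analyzed as non-diagnostic procedure"; the remainder, those with a contraindication, are screen failures. The cause goes on the case report form.
- **Section 5, last paragraph.** Attendees who "do not undergo the procedure for reasons other than safety will be analyzed on an intention-to-treat basis", with a pointer back to 4.7. It does not say what happens to the safety cases. The same paragraph makes consented patients found ineligible before the procedure is initiated screen failures.

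Section 6.2 makes the per-protocol population primary and lists no exclusions from it. The ITT analysis is a secondary sensitivity analysis that includes all randomised patients and scores dropouts without final data as failures.

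The arms differ in anesthesia. For bronchoscopy (NB): "Procedures will be performed under general anesthesia with neuromuscular blockade". For CT-guided biopsy: "Patient analgesia with local anesthesia and moderate conscious sedation will be used".

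**The concern.** *Complication*, *contraindication under institutional policy* and *safety* are not the same set, and all three depend on whether the patient has undergone the procedure, which is left undefined. Where they overlap, the label decides whether a patient stays in the denominator as a failure or leaves the analysis. The label is given after randomisation by people who know the arm.

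Removing a patient who would otherwise be a failure raises the observed accuracy of that arm. If this happens more often in NB than in CT, the comparison moves toward non-inferiority. The arms are small enough that one or two patients can matter.

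**Working it through.** **1. The rules side by side**

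| Attendee without tissue | 4.6/4.7 complication sentence | 4.7 item 3 | Section 5 |
|---|---|---|---|
| Contraindication found on arrival, nothing begun | Not engaged | Screen failure | Safety case, or ineligible before initiation: screen failure |
| Cancelled for logistics | Not engaged | Non-diagnostic | Analysed by ITT |
| Team declines on the day over a safety worry that policy does not list | Not engaged | Non-diagnostic | Safety case, destination not stated |
| Instability after induction, before the bronchoscope is in | Non-diagnostic, if called a complication | Screen failure, if called a contraindication and the procedure not undergone | Safety case, if the procedure is taken as not undergone |
| Aborted for oxygen, heart-rate or ECG change (Section 7.3), no tissue yet | Non-diagnostic | Applies only if the procedure is taken as not undergone | Same condition |

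The first two rows agree across sections. The last three can be scored in two ways.

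**2. The plan's own figures**

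Inputs from Section 6.1: "The non-inferiority margin is set at 10 percentage points", one-sided error 5%, 90% accuracy in both arms, power about 80%.

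- n per arm = (1.645 + 0.842)² × (0.90×0.10 + 0.90×0.10) / 0.10² = 111.3, so **112**, as stated.
- Power at 112 = Φ(0.10/√(0.18/112) − 1.645) = Φ(0.849) = **80.2%**.
- 112 × 1.15 = 128.8, so **129** per group, as stated.

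Rule in Section 6.2: independent Beta(1,1) priors, and non-inferiority if the posterior probability that NB is more than 10 points below CT is under 5%. Summing exactly over all binomial outcomes at n = 112 per arm with fixed true rates:

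- CT 90%, NB 80%: **5.3%** (Section 6.2 table: 5.4)
- CT 90%, NB 90%: **80.1%** (Section 6.1: about 80%)

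Section 6.2 describes its table as drawing the true rates from Beta distributions with sd 0.03. Doing that gives about 11% at 90/80, so the table row matches the fixed-rate calculation. Everything below uses fixed rates.

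**3. Effect of removal**

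True accuracy is CT 90% and NB 80% when safety stops count as failures, which puts the difference at the margin. If a share c of an arm's attendees is removed and all were failures, observed accuracy = true accuracy / (1 − c). The documents give no value for c, so every c here is an **assumption**.

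| Removed NB / CT | n NB / CT | Observed NB / CT | Difference (points) | Chance of concluding non-inferiority |
|---|---|---|---|---|
| 0 / 0 | 112 / 112 | 80.0 / 90.0 | −10.0 | 5.3% |
| 1% / 0 | 111 / 112 | 80.8 / 90.0 | −9.2 | 7.3% |
| 2% / 0 | 110 / 112 | 81.6 / 90.0 | −8.4 | 10.3% |
| 2% / 1% | 110 / 111 | 81.6 / 90.9 | −9.3 | 7.3% |
| 3% / 1% | 109 / 111 | 82.5 / 90.9 | −8.4 | 10.0% |
| 5% / 1% | 106 / 111 | 84.2 / 90.9 | −6.7 | 18.7% |
| 3% / 3% | 109 / 109 | 82.5 / 92.8 | −10.3 | 4.8% |
| 5% / 5% | 106 / 106 | 84.2 / 94.7 | −10.5 | 4.3% |
| 1% / 3% | 111 / 109 | 80.8 / 92.8 | −12.0 | 2.1% |

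**4. One patient**

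Take CT at 101/112 and NB with 97 successes. At 97/112 the posterior probability of inferiority is 6.7%, and non-inferiority is not concluded. Remove one NB failure: at 97/111 it is 4.6%, and non-inferiority is concluded.

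**The case against.** The strongest reply is that the sections fit together. Section 5 defers to 4.7 for details. A contraindication to biopsy or to deep sedation or general anesthesia is already exclusion criterion 5, so one discovered on the day makes the patient ineligible, and both 4.7 item 3 and Section 5 lead to screen failure. Anything that happens once the procedure is under way is a complication and counts as non-diagnostic. This reading is coherent, and it deals with clear contraindications. It does not deal with the cases in between: the protocol does not mark where the procedure starts, and *safety* is a wider word than *contraindication*.

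A second reply is that the direction is not established. Exclusion 5 screens both arms for anesthetic fitness before randomisation, CT-guided biopsy has its own abort rule in Section 7.3, and no cancellation rate by arm is given. That is correct. Against it, screening before randomisation cannot balance problems that appear on the day. Section 7.3 also places the greatest bronchoscopy risks in sedation and in manipulating the scope. Asymmetry is therefore plausible, but it remains an inference.

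A third reply is that the ITT analysis in Section 6.2 keeps every randomised patient. It does on its wording, but it is secondary, and the screen-failure label in 4.7 and Section 5 conflicts with it.

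**Conclusion.** The point holds as an ambiguity in the scoring rules. The same randomised attendee can be a failure or be removed, and neither the per-protocol set, which has no listed exclusions, nor the secondary ITT analysis settles which.

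The size depends on assumed removal rates. One-sided removal of 2% of NB, about two of 112 patients, roughly doubles the error at the margin, from 5.3% to 10.3%. Removal of 3% of NB and 1% of CT gives 10.0%. Equal removal does not raise it, and more removal in CT lowers it. The figures also assume that every removed patient falls in the overlap and would otherwise have been a failure.

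A reader might infer two stronger claims that the documents do not support:

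- *That 4.6 and 4.7 make every safety cancellation a failure while Section 5 removes them all.* Item 3 of 4.7 itself removes contraindication cases, and Section 5 never says where safety cases go.
- *That general anesthesia concentrates such patients in NB, so the trial is biased toward non-inferiority.* The difference in anesthesia makes this plausible, but no rates are given.

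**What to change.** - Reconcile 4.7 item 3 and Section 5 to a single term, and state that the complication sentence in 4.6 and 4.7 takes precedence.
- Define procedure start for analysis purposes, for example as the start of sedation or anesthesia in either arm. Any later stop without tissue is then non-diagnostic in the assigned arm.
- Do not label randomised attendees screen failures. Keep them in the ITT set as failures, in line with Section 6.2.
- Add a sensitivity analysis of the primary endpoint that scores every randomised attendee without a biopsy, whatever the reason, as non-diagnostic.
- Tabulate by arm the reasons for leaving without a biopsy.

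Scoring never-attempted contraindication cases as failures in the per-protocol primary analysis is debatable, because it changes the question that analysis asks. Those cases belong in the ITT and sensitivity analyses.

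The cost is a few sentences in the protocol, which the separate analysis plan announced in Section 6.2 can carry through, plus one more analysis. Observed accuracy may be slightly less favourable. Patient care does not change, only how patients are counted.
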